Multicenter Double-Blind Placebo-Controlled Parallel-Group Randomized Clinical Trial of Efficacy and Safety of Rengalin in the Treatment of Cough in Patients with Chronic Obstructive Pulmonary Disease

Phase IV

Sponsor

OOO «NPF «MATERIA MEDICA HOLDING»

Protocol numberMMH-RN-005Version date:October 17, 2016ClinicalTrials.gov Id:NCT03159091

Protocol Summary

This document represents the protocol summary for the study on human subjects. The study will be carried out in accordance with ICH GCP, National Standard of the Russian Federation GOST 52379-2005 "Good Clinical Practice", Helsinki Declaration of World Medical Association, relevant requirements of the regulatory authorities as well as the study procedures.

Title of Study

Multicenter double-blind placebo-controlled parallel-group randomized clinical trial of efficacy and safety of Rengalin in the treatment of Cough in patients with chronic obstructive pulmonary disease.

Phase: IV

Sponsor: OOO "NPF "Materia Medica Holding", Moscow, Russia *Protocol No.* MMH-RN-005

Objective of the study

• To obtain additional data on the efficacy and safety of Rengalin in the treatment of cough in patients with stable chronic obstructive pulmonary disease (COPD).

Endpoints

Primary endpoint

 Percentage of patients with a positive response after 4 weeks of the treatment (response criterion is the reducing of the Total Cough Severity Score (TCSS)* by ≥1 compared to baseline).

* according to the 12-point of the Cough Severity Scale.

Secondary endpoints

- 1. Severity of cough (TCSS according to the Cough Severity Scale) after 4 weeks of the treatment compared to baseline.
- Percentage of patients with ≥50% lesser cough severity (according to TCSS) after 4 weeks of the treatment.
- 3. The severity of the clinical symptoms of COPD (according to COPD Assessment Test [CAT]) after 4 weeks of the treatment.
- 4. Percentage of patients with no exacerbation of COPD¹ within 4 weeks of the treatment.

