If a patient meets the inclusion criteria and does not have any exclusion criteria at Visit 1 (Day 1), he/she is randomized to one of 2 groups: group 1 patients will receive Rengalin at 2 tablets 3 times a day for 4 weeks; group 2 patients will receive placebo using Rengalin dosing regimen for 4 weeks.

The patient will be monitored for 4 weeks (screening, randomization before day 1, treatment for 4 weeks). During follow-up period two visits are scheduled: Visit 1 (Day 1) and Visit 2 (Week 4) at which objective examination, recording cough severity (using TCSS) will be carried out, COPD effect on the subjects (CAT) and concomitant therapy will be evaluated. At Visit 2 (after 4-week treatment period) compliance will be additionally assessed.

² Condition may be considered stable where no disease progression is observed for ≥ 6 months [7, 20].

³ Allowed basic therapy for stable COPD: anticholinergics, long- and short-term β 2-agonists, inhalation glucocorticosteroids (ICS), methylxanthines and their combinations.

At one of the clinical sites (Research Institute of Pulmonology, Russian FMBA), patients will be monitored for cough on a daily basis (using the WHolter[™] monitor), with the data used as an additional measure to evaluate efficacy.

Patients are allowed to take basic COPD therapy and medications for their comorbidities in the course of the study, except for the medicines listed in "Prohibited concomitant treatment".

Inclusion and exclusion criteria

Inclusion criteria

- 1. Patients of either gender aged from 40 to 80 years.
- COPD (in accordance with the GOLD-2014 guidelines) diagnosed ≥12 months before inclusion.
- 3. Stable COPD (≥ 6 weeks free of disease progression).
- Mild, moderate or severe degree of airflow limitation (FEV₁/FVC < 0.7; post-bronchodilator FEV₁ ≥30% of predicted value).
- 5. TCSS score ≥ 2 .
- 6. Stable dose of standard therapy within the previous 4 weeks.
- 7. Use of and adherence of contraceptive methods by patients of reproductive age of both genders during the study.
- 8. Availability of signed patient information sheet (Informed Consent form) for participation in the clinical trial.

Exclusion criteria

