Body weight measurement	+	
Measurement of body length/height	+	

	17-Oct-2016	
Procedure/day	Visit 1 (Day 1)	Visit 2 (Week 4±3 days)
Body mass index calculation	+	
Evaluation of cough severity (according to Cough Severity Scale)	+	+
Evaluation of COPD impact on the subject's life (CAT)	+	+
Pregnancy test	+	
Concomitant therapy	+	+
Computer spirometry* (evaluation of FEV1/FVC and post-bronchodilator FEV1)	+	
Eligibility assessment	+	
Randomization and prescription of study drug	+	
Study drug supply	+	
Study drug accountability, compliance assessment		+
Evaluation of treatment safety	+	+
24-hour cough monitoring**	+ **	+ **

* Where spirometry cannot be performed, spirometry parameters dating no more than 3 months will be recorded in CRF results. ** Performed in Institute of Pulmonology, EMPA of Pussia

** Performed in Institute of Pulmonology, FMBA of Russia.

Statistical Analyses.

Samples

Total set: all patients included in the study who have signed Informed Consent Form for participation in the study. All AEs including those occurred prior to the study therapy will be considered throughout the study for this sample.

Safety population: all patients who received at least one dose of the study drug. This sample will be used to *analyze the study treatment safety and tolerability*, since all the AEs identified after the study drug administration will be recorded.

Full Analysis Set. This sample includes all enrolled and randomized patients, except for those who met at least one of the following criteria:

- 1) non-compliance with inclusion / exclusion criteria;
- 2) the patient has not taken as minimum a single dose of the study drug;
- 3) lack of any data of the patient following randomization;

This sample is the most consistent with the "Intention-to-treat" principle, will be used for the *Intention-to-treat analysis (ITT analysis) of the the study therapy efficacy*.

Per protocol set. This sample includes all patients who completed the therapy as per the study protocol without any missing visits or significant protocol deviations. This sample will be used for the *Per Protocol analysis (PP- analysis) of the the study therapy efficacy*.

Mean value of the total set for the relevant day will be used to fill lacking/missing data.

Data treatment and all statistical calculations under the protocol will be made using SAS-9.4 statistical software⁴.

Evaluation of sample size

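### In the ITT analysis a pooled-mean fill, not the patient's outcome, sets responder status for many leavers, and the Full Analysis Set drops or fills them according to what record they left

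*Combined protocol and SAP*

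**What the plan says.** Under Statistical Analyses, Samples, the FAS is assigned to the ITT efficacy analysis. It leaves out randomised patients on three grounds: "non-compliance with inclusion / exclusion criteria", "the patient has not taken as minimum a single dose of the study drug" and "lack of any data of the patient following randomization". Because not taking a dose is a separate ground, the third can remove patients who were treated. The same section closes with the fill rule: "Mean value of the total set for the relevant day will be used to fill lacking/missing data". The total set is defined there as everyone who signed consent, so the mean is taken over both arms.

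The primary endpoint is a fall of at least 1 point in the Total Cough Severity Score (TCSS) at 4 weeks. Secondary endpoint 2 is a 50% reduction on the same scale. The Study design section and the Schedule of study procedures show one visit after baseline (Week 4) and no early-termination visit. In the schedule, drug is supplied at Visit 1, but "Study drug accountability, compliance assessment" is marked only at Visit 2.

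The withdrawal criteria include exacerbation, an adverse event requiring discontinuation, and leaving for lack of efficacy. The exacerbation footnote under Endpoints says that an exacerbation is recorded as an adverse event. Evaluation of sample size allows for at least 20% withdrawal. The Per Protocol set takes patients who completed therapy "without any missing visits or significant protocol deviations".

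**The concern.** A patient who leaves before Week 4 has no TCSS from which to judge response. The plan supplies one from the mean of everybody else, whatever the reason for leaving. If the fill is applied to the score, a leaver becomes a responder when baseline TCSS minus the pooled Visit 2 mean is at least 1. That depends on the baseline score and not on what happened to the patient. The text does not say whether the score or the responder status is filled.

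The third FAS exclusion adds a second split. A leaver with an exacerbation or other adverse event on record has data, stays in and is filled. A patient who simply stops coming has none and is dropped. So handling depends on the record that the departure left, which can be linked to the reason for leaving. The phrase is also ambiguous: it may mean no data at all or some item missing, and the primary denominator changes with the reading.

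The ITT result is meant to preserve the randomised comparison. If withdrawal, or the record it leaves, differs between arms, these rules can create or hide a difference in the primary endpoint.

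**Working it through.** **The plan's own figure.** Inputs from Evaluation of sample size: two-sided 5%, power 80%, difference 0.20, 1:1 allocation, and the rates that give the largest sample, which are 0.60 vs 0.40. n = (1.960 + 0.842)² / 0.20² × (0.24 + 0.24) = 94.2, so 95 per group. Then 190 / 0.8 = 237.5, so 238 (119 per group). The figure reproduces and is not in dispute.

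**How many patients the rules govern.** Taking all 119 per arm as randomised, 20% withdrawal gives 23.8 leavers per arm. If a quarter leave no record, about 6 are dropped and about 18 are filled.

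**What share of filled leavers would count as responders (g).** The documents give no TCSS distribution. I assume whole-number baseline scores of at least 2 (the entry minimum), baseline means of about 3 to 6 (standard deviation 1 to 2) and mean falls of 0.5 to 2. Simulation then gives g of about 0.31 to 0.69. Example: with baseline mean 5.06 and mean fall 1, the Visit 2 mean is 4.06. A leaver with baseline 6 is scored a responder (6 − 4.06 = 1.94). One with baseline 5 is not (0.94). Here g is about 0.40.

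**Null case A (assumed).** 40% of all randomised respond in both arms, no leaver responds, and withdrawal is d = 15% vs 25%. Let f be the share of leavers dropped.

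Rate = (0.40 + g(1 − f)d) / (1 − fd), with n = 119(1 − fd), compared by a two-sided pooled z-test.

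For f = 0.25 and g = 0.5:
- 15% arm: (0.40 + 0.05625) / 0.9625 = 0.474, n = 114.5
- 25% arm: (0.40 + 0.09375) / 0.9375 = 0.527, n = 111.6

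| f | g | rates | rejection |
|---|---|---|---|
| 0.10 | 0 (exclusion alone) | 0.406 vs 0.410 | 5.1% |
| 0.25 | 0 (exclusion alone) | 0.416 vs 0.427 | 5.3% |
| 0.25 | 0.31 | 0.452 vs 0.489 | 8.6% |
| 0.25 | 0.5 | 0.474 vs 0.527 | 12.4% |
| 0.25 | 0.69 | 0.496 vs 0.565 | 17.7% |
| 0.25 | 1 | 0.533 vs 0.627 | 29.9% |
| 1 | any (all leavers dropped) | 0.471 vs 0.533 | 13.8% |
| 0 | 1 (exclusion removed, fill kept) | 0.55 vs 0.65 | 34.9% |

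With 20% withdrawal in both arms, every case gives 5.0%.

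**Null case B (assumed).** Completers respond at 50% in both arms, with withdrawal again 15% vs 25%.
- Plan's rule, f = 0.25: 5.0% at g = 0.5, about 5.6% at g = 0.31 or 0.69, and 9.7% at g = 0 or 1.
- Non-responder counting: 0.5 × 0.85 = 0.425 vs 0.5 × 0.75 = 0.375, rejection 12.3%.

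**Power (assumed completers 60% vs 40%, 20% withdrawal, 119 per arm).**
- Non-responder counting: 0.48 vs 0.32, power 71.5%.
- Plan's rule, f = 0.25, n = 113 per arm: 0.505 vs 0.337 at g = 0 (73.0%), and 0.584 vs 0.416 at g = 0.5 (71.9%).

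**The case against.** The strongest reply is that the FAS exclusion does little harm. Read narrowly, it moves rejection only to 5.1-5.3%, and while the fill stays it slightly dampens the larger problem (30% with it, 35% without, at g = 1). This stands, and it is why the fill rule carries the weight here. A reader might infer that the exclusion by itself undermines the ITT analysis. The documents support that only if most leavers have no record, or if the phrase is read to cover any missing item.

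Second, null case A favours non-responder counting. Fixing 40% among all randomised with no response among leavers forces completers to 47% vs 53%. In case B the plan's rule does better than the fix. This also stands.

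Third, a reader might take 30% or 35% as the expected error rate. Both need every filled leaver to score as a responder, and nothing in the documents points to that or to unequal withdrawal.

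Fourth, the rule turns on whether data exist, not on the reason for leaving. If a recorded reason for withdrawal counts as data, only silent losses are dropped. The link to reason is therefore an inference. The text also says of itself "This document represents the protocol summary for the study on human subjects", so definitions or an early-termination visit may exist in the full protocol.

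None of this justifies filling a responder endpoint with a pooled mean.

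**Conclusion.** The point holds for the fill rule, with the FAS exclusion as a secondary part. As written, patients who left for exacerbation, an adverse event or lack of efficacy can be counted as responders on the primary endpoint, and similar leavers can be filled or dropped according to what was recorded.

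Under case A with a quarter of leavers dropped, two-sided rejection is about 9-18% over the plausible range of g, against a nominal 5%. This rests on assumed response rates, an assumed 10-point gap in withdrawal and an assumed TCSS distribution. With equal withdrawal there is no inflation.

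A reader might infer that the rule favours Rengalin. The documents do not support that: the direction depends on which arm loses more patients and on how the filled values score, and neither is known. The plan should be changed before unblinding. Confidence in the size is moderate at best.

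**What to change.** 1. For the primary endpoint and secondary endpoint 2, count every FAS patient without a Visit 2 TCSS as a non-responder, in place of the mean fill. Reconcile this with the exacerbation footnote, which says that a first-week exacerbation is not considered a secondary inefficacy criterion.
2. Together with step 1, and not while the mean fill stays, keep dosed patients with no later record in the FAS as non-responders. Since dosing is checked only at Visit 2, state that patients supplied with drug at Visit 1 and not seen again are treated as dosed.
3. Name the already planned Per Protocol analysis as the sensitivity result.
4. State the power for the FAS.

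The cost is wording only, with no new data or enrolment. Non-responder counting is not neutral: if completers respond equally and withdrawal is 15% vs 25%, rejection is about 12%, against 5-10% under the plan's rule. That is why the Per Protocol result should stand beside it. At 20% withdrawal, FAS power is about 71%, against about 72-73% under the existing rule with a quarter of leavers dropped. Most of the shortfall from 80% therefore comes from item 1.8, which sizes the trial on completers, and not from the change. The continuous endpoints need their own missing-data rule, which this point does not cover.

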¹ COPD exacerbation is defined as an acute event characterized by aggravation of the event within 2-3 or more days. Exacerbation manifests in intensification of respiratory disorders beyond their regular daily fluctuations and require administration of products in addition to the previously prescribed basic therapy as well as a rescue drug for symptom relief (salbutamol). Additional products include antibacterial drugs, systemic corticosteroids and/or emergency therapy (ambulance call) or hospitalization for COPD exacerbation.

COPD exacerbation is recorded as an adverse event. If a COPD exacerbation develops within the first week of the subject participation in the study, it will not be considered as a secondary inefficacy criterion.

 Frequency of cough and other respiratory patterns according to 24-hour daily monitoring (using WHolterTM) after 4 weeks of the treatment compared to baseline.

Safety assessment

- Adverse events (AEs) during the treatment, AEs severity and relations to the study drug, and AEs outcomes.
- Changes in vital signs.

Study design

Study design: multicenter, double-blind, randomized, parallel group placebo-controlled study.

The study will enroll men and women (aged 40 to 80 years) with cough associated with stable $COPD^2$. Subjects with COPD diagnosed more than 12 months earlier obtaining allowed basic therapy³ and retaining cough ≥ 2 points (according to Cough Severity Scale [CSS]) despite their therapy should be considered as the study candidates.

After signing patient information sheet (informed consent form) to participate in the clinical trial, medical history and objective examination are performed, cough severity is assessed (using TCSS; at baseline evaluation of diurnal and nocturnal cough the number of episodes and cough severity in the preceding day is taken into account) as well as intensity of COPD effect on the subject (CAT test), concomitant therapy is recorded, computer spirometry with evaluation of baseline FEV₁/FVC and post-bronchodilator FEV₁ (where respiratory function cannot be assessed, the results of the previous examination dating no more than 3 months earlier may be used). Females of childbearing potential will undergo pregnancy test.

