- 24. Patient is a study specialist of the centre and directly involved in the study, or is an immediate family member of the Investigator. Spouses, parents, children, or siblings, regardless of whether they are siblings or adopted are considered immediate family members.
- 25. The patients work for OOO "NPF "Materia Medica Holding", i.e. they are employees of the Company, temporary employees on a contract basis or appointed officials responsible for conduction of the study or their immediate family members.

Criteria for Withdrawal or Termination

- 1. COPD exacerbation.
- 2. The patient's inability or refusal to follow the protocol requirements.
- 3. The necessity to use medications prohibited within this trial.

- 4. Change in the stereotype of smoking (ceasing smoking for smokers, starting smoking for non-smokers).
- 5. An adverse event requiring discontinuation of the study drug.
- 6. Patients wish to complete the study ahead of schedule due to lack of treatment efficacy or for any other reason.
- 7. Cases not specified by the protocol when, according to the investigator's opinion, further participation in the study harms the patient.
- 8. Incorrect inclusion of ineligible patient.
- 9. Patient failed screening procedure.

Number of subjects

At least 238 patients will be enrolled, which is expected to yield at least 190 patients (95 x 2 groups (Rengalin and Placebo) completing all protocol procedures.

Interim analysis

An interim statistical analysis is not scheduled within the study.

Treatment

Group 1

Name of the medicinal product: Rengalin

Active ingredient: affinity purified antibodies to bradykinin -0.006 g*, affinity purified antibodies to histamine -0.066 g*, affinity purified antibodies to morphine -0.066 g*

* *Mixture of water-ethanol dilutions* 100^{12} , 100^{30} , 100^{50} of active substance used for saturation of isomalt.

Excipients: isomalt 0.506 g, microcrystalline cellulose 0,0275 g, magnesium stearate 0.0055 g, anhydrous citric acid 0.005225 g, colloidal anhydrous silica 0.00275 g, sodium cyclamate 0.00275 g, sodium saccharin 0.000275 g.

Method of administration: Tablet for oral use. Two tablets per intake. The tablet should be held in the mouth until complete dissolution. 2 tablets 3 times a day without food (i.e. 15-30 min prior to meal or 15-30 min after meal).

Dosage form: Tablets.

Description: White to off-white, round, flat, cylinder-shaped, beveled edge tablets scored on one side, with integral edges.

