Storage conditions: Store in a place protected from light, at the temperature not exceeding 25°C. Keep out of the reach of children.

Group 2

Name of the medicinal product: Placebo

Active ingredient: NA

Excipients: isomalt 0.506 g, microcrystalline cellulose 0,0275 g, magnesium stearate 0.0055 g, anhydrous citric acid 0.005225 g, colloidal anhydrous silica 0.00275 g, sodium cyclamate 0.00275 g, sodium saccharin 0.000275 g.

Method of administration: Placebo using Rengalin scheme.

Dosage form: Tablets.

Description: White to off-white, round, flat, cylinder-shaped, beveled edge tablets scored on one side, with integral edges.

Storage conditions: Store in a place protected from light, at the temperature not exceeding 25°C. Keep out of the reach of children.

Treatment duration

Rengalin/Placebo treatment duration is 4 weeks.

Observation period

In total, the patient is observed up for 4 weeks (screening + randomization up to 1 days, study therapy for 4 weeks).

Symptomatic (Standard) treatment

During the study the subjects may receive basic COPD therapy (anticholinergic drugs, β 2-agonists, IGCS, methylxanthines and their combinations) and therapy of co-morbidities not referred to exclusion criteria.

Prohibited concomitant therapy

For 4 weeks prior to inclusion and during the study (from the time of signing the information sheet (Informed Consent Form) and screening initiation), it is prohibited to use the following medications:

- 1. Expectorant (R05CA), mucolytic (R05CB), antitussive (R05D) medicines and their combinations (R05F).
- 2. Fenspiride (erespal) (R03DX).
- 3. Icatibant (firazyr) (C01EB19).
- 4. Systemic antihistamines (R06).
- 5. Cold medicines (R05X).
- 6. ACE inhibitors (C09A) and their combinations (C09B).
- 7. Systemic glucocorticosteroids (H02AB).

- 8. Drug products that irritate or suppress the cough centre in the CNS or produce such side effects, as described in the instruction.
- 9. Centrally acting muscle relaxants (M03B).
- 10. Antibacterial medicines for systemic use (J01).
- 11. The products of the company Materia Medica Holding.
- 12. Homeopathic remedies.
- 13. Drugs known to previously cause allergic reactions in the patient.

Study design scheme

Schedule of study procedures

Procedure/day	Visit 1 (Day 1)	Visit 2 (Week 4±3 days)
Informed consent	+	
Collection of complaints	+	+
Medical history	+	
Physical examination and vital signs (heart rate, respiratory rate, blood pressure, body temperature)	+	+

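### The Per Protocol analysis of secondary endpoint 4 (no COPD exacerbation) excludes essentially every patient who has the event, so it shows about 100% in both arms whatever the drug does

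*Combined protocol and SAP*

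**What the plan says.** All references are to the combined protocol and SAP.

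- **Secondary endpoints, item 4:** "Percentage of patients with no exacerbation of COPD¹ within 4 weeks of the treatment".
- **Footnote 1 to that item:** an exacerbation needs treatment beyond basic therapy and the rescue drug. "Additional products include antibacterial drugs, systemic corticosteroids and/or emergency therapy (ambulance call) or hospitalization for COPD exacerbation". It is recorded as an adverse event. One that develops in the patient's first week in the study does not count as inefficacy (the first-week rule).
- **Criteria for Withdrawal or Termination:** the list opens with "1. COPD exacerbation", without limits on timing or severity. It also includes "3. The necessity to use medications prohibited within this trial".
- **Prohibited concomitant therapy, items 7 and 10:** systemic glucocorticosteroids and systemic antibacterials are both barred during the study.
- **Statistical Analyses, Samples, Per protocol set:** "This sample includes all patients who completed the therapy as per the study protocol without any missing visits or significant protocol deviations". The set is used for the per-protocol analysis of efficacy, with no endpoint exempted.
- **Same section, Full Analysis Set:** there are three grounds for exclusion: failing the eligibility criteria, taking no dose, and having no data after randomization. Exacerbation is not among them.

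**The concern.** Membership of the Per Protocol set depends on the outcome that endpoint 4 measures. Patients with the event are selected out, and those who remain are event-free because of the selection.

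A per-protocol table showing about 100% exacerbation-free in both arms could be read as a good clinical result, or as evidence of no difference between arms. It would be neither. It could not corroborate or contradict the Full Analysis Set result, which is the usual purpose of a per-protocol analysis. If the two sets disagreed, a reader might wrongly conclude that a Full Analysis Set effect was fragile. If the drug increased exacerbations, the per-protocol table would not show it.

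**Working it through.** **1. Are withdrawn patients outside the Per Protocol set?** The sample size section answers this. Item 1.8 sets N_T = N_PP / (1 − C_w), where N_PP is the number finishing per protocol and C_w is the withdrawal coefficient. The plan's figures reproduce:

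- n = (1.960 + 0.842)² / 0.2² × [0.6 × 0.4 + 0.4 × 0.6] = 94.19, rounded up to 95 per group. The pair 0.6 and 0.4 is inferred from the stated conservative approach.
- 95 / (1 − 0.20) = 118.75, rounded up to 119 per group, 238 in total.

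The plan thus subtracts withdrawn patients from those enrolled to reach the per-protocol number.

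**2. The chain.** Exacerbation → withdrawal (criterion 1) → 4-week therapy not completed → not in the Per Protocol set. Exacerbations treated with antibacterials or systemic corticosteroids also meet criterion 3, because both classes are prohibited.

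**3. Does the first-week rule change this?** No. An early exacerbator is either withdrawn, and so outside the set, or kept and not counted as a failure. Neither adds an event to the Per Protocol set.

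**4. Illustration.** The rates are assumed, since the documents give none. The arm size is 119, the number per group required to consent, so it is an upper limit for any analysis set. The table ignores the first-week rule, other dropout and the late leak.

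| Assumed 4-week risk (Rengalin vs placebo) | Exacerbation-free, all counted | Exacerbation-free, Per Protocol |
|---|---|---|
| 2% vs 5% | 117/119 = 98.3% vs 113/119 = 95.0% | 117/117 vs 113/113 |
| 5% vs 10% | 113/119 = 95.0% vs 107/119 = 89.9% | 113/113 vs 107/107 |
| 5% vs 15% | 113/119 = 95.0% vs 101/119 = 84.9% | 113/113 vs 101/101 |
| 10% vs 20% | 107/119 = 89.9% vs 95/119 = 79.8% | 107/107 vs 95/95 |

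In the 5% vs 10% row, 119 × 0.05 ≈ 6 and 119 × 0.10 ≈ 12 exacerbations are removed. Removing a further 10% of patients for other reasons leaves the Per Protocol column at 100% vs 100%. A Fisher test on tables with no events gives p = 1.

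**5. With the first-week rule.** If events are spread evenly over 4 weeks (assumption), one quarter do not count. The countable events are 0.75 × 119 × 0.05 ≈ 4.5 and 0.75 × 119 × 0.10 ≈ 9. Counting all patients, the exacerbation-free proportions become 1 − 0.75 × 0.05 = 96.25% and 1 − 0.75 × 0.10 = 92.5%.

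**6. The late leak.** Suppose exacerbations starting in the last 3 of 28 days do not prevent completion (assumption, suggested by the ±3-day window for Visit 2). For true risk e, the per-protocol exacerbation-free rate is 1 − (3e/28) / [(1 − e) + 3e/28]:

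- e = 5%: 99.4%
- e = 10%: 98.8%
- e = 20%: 97.4%

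A true difference of 5 percentage points (5% vs 10%) would appear as about 0.6.

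**The case against.** **The rule is not airtight.** The withdrawal list does not say when withdrawal takes effect, and completing therapy per protocol is not closely defined. By footnote 1 an exacerbation develops over 2–3 or more days, so one that starts late or is recognised at Visit 2 could coincide with completed treatment. This stands. A reader might infer that the per-protocol result must be exactly 100% in both arms with a difference of exactly 0. The documents do not support that, because they do not rule out the late case. What they support is essentially all events removed and a rate close to 100%.

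**Withdrawal under a listed criterion is not a deviation.** True, but the set also requires completed therapy, and item 1.8 treats withdrawn patients as outside it.

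**Not every exacerbation is an endpoint event.** This stands. The first-week rule lowers the countable number, from about 6 and 12 to about 4.5 and 9 in the illustration.

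**The plan may not intend a per-protocol analysis of endpoint 4.** The document is a protocol summary and gives no list of endpoints by analysis set. That is fair, but it assigns the Per Protocol set to efficacy in general, and footnote 1 treats exacerbation as an inefficacy criterion. The text as written includes endpoint 4.

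**Little is lost.** The Full Analysis Set keeps exacerbators, and exacerbations also appear as adverse events. In the illustration, 6/119 vs 12/119 gives z ≈ 1.5 and p ≈ 0.14, so the full comparison would not be significant either. This limits the importance of the point. It does not make the per-protocol figure meaningful.

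**Conclusion.** The point holds, with a narrow scope. Under the written rules the Per Protocol analysis of secondary endpoint 4 excludes essentially all patients with the event and shows about 100% exacerbation-free in both arms, whatever the drug does. Allowing for late events in the last 3 of 28 days, the rate would still be 97.4% to 99.4% at true risks of 20% to 5%.

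The conclusion rests on withdrawal criterion 1 being applied as listed and on completed therapy meaning the 4-week course. The event counts and percentages rest on assumed risks and, where stated, on events spread evenly over time.

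A reader might infer that endpoint 4 cannot be tested at all, or that exacerbation data are lost. The documents do not support this. The Full Analysis Set does not exclude exacerbators, and its analysis can show a difference if events in withdrawn patients are counted. Adverse event reporting is intact. The primary endpoint is a different outcome, and its sample size reproduces and is unaffected. The defect is confined to one analysis set for one secondary endpoint.

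**What to change.** In the Samples section, state that secondary endpoint 4 is analysed on the Full Analysis Set only, that exacerbations in withdrawn patients count as events subject to the first-week rule in footnote 1, and that endpoint 4 is not part of the Per Protocol analysis.

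An alternative would keep in the Per Protocol set those patients whose only reason for not completing was an exacerbation, and count them as events. It is not recommended. Many of them would also have needed prohibited antibacterials or systemic corticosteroids, so an only-reason condition would drop many of the events it aims to restore. Without a timing limit it would also conflict with the first-week rule.

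The cost is a sentence or two of analysis wording. No extra patients or data are needed, since exacerbations are already recorded as adverse events, and the withdrawal criteria are left as they are.
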